Study Title: Technology Intensified Diabetes Education Study in African Americans With Type 2 Diabetes

NCT02088658

Document Date: December 13, 2016

SPECIFIC AIMS

Diabetes Mellitus affects approximately 24 million adults in the United States (NIH 2008). African Americans (AA) with Type 2 diabetes (T2DM) have higher prevalence of diabetes, poorer metabolic control and greater risk for complications and death compared to White Americans (NIH 2008). There is strong evidence that self-management interventions that include diabetes education and skills training are effective at improving metabolic control in diabetes (Norris 2002). Recent findings indicate that patients with diabetes, especially ethnic minority patients, prefer telephone-delivered diabetes education to group visits or internet-based education (Sarkar 2008). Preliminary data from our group suggest that a culturally-tailored telephone-delivered diabetes education and skills training intervention (Egede 2010) is an effective strategy to improve metabolic control in AA patients with T2DM. However, no large RCT has tested whether providing feedback to patients using novel technology like the FORA 2-in-1 Blood Glucose and Blood Pressure monitor leads to improvements in glycemic and blood pressure control or whether using the feedback to tailor and augment diabetes education and skills training are effective at improving metabolic control.

Aim 1: To test the efficacy of a technology-intensified diabetes education/skills training (TIDES) intervention using the FORA 2-in-1 and Telehealth System for diabetes in improving HbA1c levels in AAs with poorly controlled T2DM.

Aim 2: To test the efficacy of the TIDES intervention in improving BP control and quality of life in AAs with poorly controlled T2DM.

RESEARCH STRATEGY

Approach. The overarching aim of this proposal is to test the efficacy of a technology-intensified diabetes education/skills training (TIDES) intervention in AAs with poorly controlled T2DM. 200 patients will be randomly assigned to two groups of 100 patients each; TIDES intervention group and usual care group. Each patient will be followed for 12 months, with study visits at baseline, 3, 6, 9, and 12 months. The primary outcome will be HbA1c at 12 months post-randomization while the secondary outcomes will be blood pressure control and quality of life at 12 months post-randomization.

Study Population & Recruitment Plan

The study sites for this study are MUSC general medicine, endocrine, family medicine, and community primary care clinics. The investigative team has access to patients in these clinics and letters of support from key physician collaborators in each of these clinics are attached.

Patient eligibility criteria: The study inclusion and exclusion criteria are as follows

Inclusion Criteria: 1) Age ≥ 21 years; 2) Clinical diagnosis of T2DM and HbA1c $\geq 8\%$ at the screening visit; 3) Self-identified as AA; 4) Subject must be willing to use the FORA monitoring system for 12 months; 5) Subjects must be able to communicate in English; and 6) Subjects must have access to a telephone (landline for data uploads) for the study period.

Exclusion Criteria: 1) Mental confusion on interview suggesting significant dementia; 2) Participation in other diabetes clinical trials; 3) Alcohol or drug abuse/dependency; 4) Active psychosis or acute mental disorder; and 5) Life expectancy <12 months.

Description of Intervention: Patients will be assigned the FORA 2-in-1 Telehealth System and provided glucose test strips to allow testing at least once a day. The glucose and BP readings will be used to tailor and reinforce behavior change during weekly telephone-delivered diabetes education sessions. Subjects will receive: 1) the FORA system for self-monitoring; 2) weekly telephone-delivered diabetes education/skills training; 3) patient activation; and 4) patient empowerment. The intervention will be delivered by telephone once a week for 12 weeks with each session lasting ~ 30 minutes.

Assessments: Patients will be assessed at baseline, 3-months, 6-months, 9-months, and 12-months post randomization. Assessments will include valid and reliable scales administered by the study team. Participants will receive \$25 for completing each visit.

Patient Randomization: A permuted block randomization method will be used to assign subjects to one of the two intervention groups. Block size will be varied to minimize the likelihood that the blind will be broken. The randomization will be stratified by clinical site, and baseline HbA1c levels (8-10% vs. $>10\%$).

Sample Size and Power. With 80 subjects randomized to each of the two intervention groups, we will have 85% power to detect at least a 0.4 standardized effect size (difference in comparison group means in sd units) for continuous outcome measures.

Analysis Plan

We will use a generalized linear models (GLMM) approach as the general analytic framework for inferential analyses for the Primary/Secondary efficacy aims. In addition to accommodating a wide range of distributional assumptions [dichotomous/categorical (e.g., binomial), continuous (e.g., normal), ordinal, count (e.g., Poisson)]. GLMM is equivalent to a linear mixed effect model (MEM) approach. MEM analyses estimate individual change in outcome for each subject in addition to estimating average change in outcome within each of the individual a, b, c, d intervention groups. The basic modeling procedure will involve using the longitudinal measurements of HbA1c (primary) separately as the dependent (outcome) variable, with intervention group (fixed effect), time (random effect), and time by intervention as the primary independent variables.

Project Timeline: The study duration is four years (48 months). Months 1-6 will be used for startup, Months 7-30 will be used for participant enrollment and intervention delivery, Months 31-42 will be used for participant follow-up and Months 43-48 will be used for data analysis. We will randomize 200 patients in 4 cohorts of 50 patients every 6 months with an average of 9 randomized patients per month.

PROTECTION OF HUMAN SUBJECTS

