1. RISKS TO THE SUBJECTS

a. Human Subjects Involvement and Characteristics

The overarching aim of this proposal is to test the efficacy of a technology-intensified diabetes education/skills training (TIDES) intervention in AAs with poorly controlled T2DM. 200 patients will be randomly assigned to two groups of 100 patients each; TIDES intervention group and usual care group. Each patient will be followed for 12 months, with study visits at baseline, 3, 6, 9, and 12 months. The primary outcome will be HbA1c at 12 months post-randomization while the secondary outcomes will be blood pressure control and quality of life at 12 months post-randomization.

Study clinics: The study sites for this study are MUSC general medicine, endocrine, family medicine, and community primary care clinics.

Participant Payment: Randomized participants will receive \$50 for completion of baseline, 3, 6, 9, and 12 month assessments for a total payment of \$250. Those considered ineligible at baseline will receive \$10 and not be randomized.

Patient eligibility criteria: The study inclusion and exclusion criteria are as follows

Inclusion Criteria: 1) Age ≥ 21 years; 2) Clinical diagnosis of T2DM and HbA1c $\geq 8\%$ at the screening visit; 3) Self-identified as AA; 4) Subject must be willing to use the FORA monitoring system for 12 months; 5) Subjects must be able to communicate in English; and 6) Subjects must have access to a telephone (landline for data uploads) for the study period.

Exclusion Criteria: 1) Mental confusion on interview suggesting significant dementia; 2) Participation in other diabetes clinical trials; 3) Alcohol or drug abuse/dependency; 4) Active psychosis or acute mental disorder; and 5) Life expectancy <12 months.

b. Sources of Materials

1. Research Material & Data: Sources of research material include medical history, research questionnaires, blood pressure readings, and blood specimens. The questionnaires will obtain information about demographics, clinical history, diabetes self-care, resource use, depression, and quality of life. Patients will provide ~ 10 cc of blood for laboratory testing.

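### Does it matter to the trial that the protocol gives two payments, USD 25 and USD 50, for the same five visits?

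*Protocol*

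**What the plan says.** The payment appears in two places in the protocol.

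- **Research Strategy, Assessments.** The schedule is given first: "Patients will be assessed at baseline, 3-months, 6-months, 9-months, and 12-months post randomization". The paragraph then ends with the payment, USD 25 "for completing each visit".
- **Protection of Human Subjects, section 1 (Risks to the Subjects), Participant Payment.** Randomized participants receive, again in dollars, "50 for completion of baseline, 3, 6, 9, and 12 month assessments for a total payment of" USD 250. A separate USD 10 goes to people found ineligible at baseline, who are not randomized.

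The opening of that second section repeats the visit schedule, "with study visits at baseline, 3, 6, 9, and 12 months", and the enrolment, "200 patients will be randomly assigned to two groups of 100 patients each". Both paragraphs therefore refer to the same five visits. Neither is marked as superseded, and neither restricts its amount to one arm, one type of visit or one period of the study.

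**The concern.** Two sections of one document state different amounts for the same event. What participants are paid is a human-subjects term, and here the human-subjects section disagrees with the procedures section. Staff working from different pages could pay different sums for the same visit, and nothing says which page governs.

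A statistician would ask one further question. The primary outcome is HbA1c at 12 months, so the trial depends on patients returning for a visit a year after randomization. The visit payment is the only stated inducement to return. The Sample Size and Power paragraph quotes 80 subjects per group while 100 per group are to be randomized. If the gap of 20 per group is an allowance for dropout, and if that allowance was set with one payment in mind, then halving the payment could cost follow-up and hence power. Were that chain to hold, the discrepancy would bear on the primary analysis as well as on the petty-cash ledger.

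**Working it through.** **Inputs**

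- Number of paid visits: 5 (baseline, 3, 6, 9 and 12 months), the same in both sections.
- Rate in Assessments: USD 25 per visit.
- Rate in Participant Payment: USD 50.
- Stated total in Participant Payment: USD 250 per randomized participant.
- Randomized patients: 200.

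**Step 1. Reproduce the stated total.** Total = rate x visits = 50 x 5 = USD 250, which agrees with the protocol. It also settles a possible ambiguity. The USD 50 cannot be one lump sum for all five assessments, because the total would then be 50 and not 250.

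**Step 2. Try the other rate.** 25 x 5 = USD 125, half of the stated total. Reaching 250 at USD 25 would need 250 / 25 = 10 paid visits, and only five are scheduled.

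**Step 3. Size of the gap.**

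| Rate per visit | Per completer | 200 patients, all visits attended |
|---|---|---|
| USD 25 | USD 125 | USD 25,000 |
| USD 50 | USD 250 | USD 50,000 |
| Difference | USD 125 | USD 25,000 |

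The ratio is 50 / 25 = 2. The last column is an upper limit, since it assumes that no visit is missed.

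**Step 4. Look for a reading that reconciles them.**

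- Different people? The Assessments paragraph speaks of participants without restriction, and the USD 10 for ineligible people explains neither figure.
- Two additive components? The second paragraph calls its USD 250 the total, which leaves no room for a further 125.

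No reconciling reading is left, so one of the figures is a slip.

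**Step 5. Follow the figure into the statistics.**

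- *Sample size.* The stated inputs are the number per group, a standardized effect of 0.4 and 85% power. Payment is not among them.
- *The 80 against 100.* 100 - 80 = 20 per group, or 20%. The power paragraph, however, describes the 80 as randomized, not as evaluable, and the protocol states no attrition rate. Reading the 20 as expected dropout is a guess, and tying that dropout to the size of the payment is a second guess on top of it.
- *Comparison of arms.* Neither paragraph makes the payment depend on allocation, so neither rate as written treats the groups differently.
- *Analysis.* The mixed model for repeated HbA1c uses group, time and their interaction. None of these changes with the payment.

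The discrepancy alters no statistical quantity in the protocol.

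**The case for a change.** The strongest case for acting is that the contradiction is explicit and survives every attempt to reconcile it. It lies in the protocol itself, so no separate analysis plan could resolve it. Payment to participants is also something a protocol should state once and correctly, and the correction would be a single line. All of that stands as a description of the text.

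The consequences drawn from it are weaker.

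- **Retention and power.** The protocol never describes the payment as serving retention and gives no attrition assumption for it to support.
- **What participants were promised.** That is in the consent form, which is not among the documents at hand. Two protocol paragraphs disagree, but it cannot be shown that any participant was told two amounts.
- **Ethics review.** It would be wrong to suppose that the review board saw only the human-subjects section. The Institutional IRB paragraph of the Data and Safety Monitoring Plan has the board review and approve the funded protocol together with the consent forms, so both figures were within its remit.
- **Uneven payment by staff.** This is possible but not established. One paragraph is devoted to payment, with a rate, a matching total and a rule for ineligible people. The other is a closing sentence in a short summary of assessments. Staff who want to know what to pay would naturally look to the former and to the consent form.
- **Equal payment across arms.** Neither paragraph suggests otherwise, so there is nothing to repair.

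**Conclusion.** The inconsistency is genuine and exactly twofold: USD 125 against USD 250 per completer, and at most USD 25,000 across the study. It is a clerical slip in an administrative term. Settling it either way would leave the power, the risk of bias, the estimate and the conclusions as they are, so there is no statistical gain from amending the plan.

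Only one of the two paragraphs carries a total, and that total agrees with its own rate. This makes the other sentence the likelier leftover, although the protocol does not prove it, and nothing here depends on which amount was intended. Whoever maintains the document can align the two paragraphs with the consent form as routine housekeeping.

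This conclusion rests on two assumptions: that the payment is the same in both arms, as both paragraphs read, and that the sample size was not built on a dropout rate tied to the payment, of which the protocol gives no sign.

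### The stated 85% power for 0.4 SD with 80 randomized per group does not follow from the inputs given, and 80 contradicts the 100 per group stated elsewhere

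*Protocol*

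**What the plan says.** Under Sample Size and Power, the Protocol states: "With 80 subjects randomized to each of the two intervention groups, we will have 85% power to detect at least a 0.4 standardized effect" size. It defines that effect as a "difference in comparison group means in sd units) for continuous outcome measures". The paragraph gives no significance level, sidedness, test, within-patient correlation or dropout rate, and none appears elsewhere in the document.

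The number randomized is different in every other place:

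- Research Strategy, Approach: "200 patients will be randomly assigned to two groups of 100 patients each; TIDES intervention group and usual care group". Section 1a, Human Subjects Involvement and Characteristics, says the same.
- Project Timeline: "We will randomize 200 patients in 4 cohorts of 50 patients every 6 months".
- Targeted/Planned Enrollment Table: 200 subjects.

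The endpoint is fixed under Approach: "The primary outcome will be HbA1c at 12 months post-randomization". The Analysis Plan names a longitudinal mixed model for HbA1c with group, time and their interaction. It does not connect that model to the power figure.

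**The concern.** There are two separate problems.

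1. **The power figure.** An effect defined as a difference in means in SD units, with a sample size per group and nothing else, reads as a two-sample comparison of means. On that reading 80 per group falls well short of 85% at the usual two-sided 5% level.
2. **The sample size.** Both 80 and 100 per group are described as randomized, so the totals are 160 and 200, and both cannot be true. If 80 was meant as completers after 20% loss, the protocol does not say so, and the word *randomized* is then wrong.

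This paragraph is the only justification of the trial's size, and it is the reference for interpreting a null result. If the unadjusted two-sided 5% reading is correct, the chance of missing a true 0.4 SD effect is about 29% with 80 per group (100 − 71.0) or about 20% with 100 per group (100 − 80.4). The protocol implies 15%.

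**Working it through.** **Inputs from the Protocol.** Difference d = 0.4 SD, so SD = 1 on this scale; n = 80 per group (Sample Size and Power) or n = 100 per group (Approach; section 1a); two equal groups; claimed power 85%.

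**Assumed, because not stated.** Alpha 5%, tried two-sided and one-sided; no covariate adjustment; one measurement per patient.

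**Step 1: try to reproduce the 85%.** In the normal approximation, power = Φ(d·√(n/2) − z). The last column is the exact figure from the noncentral t distribution.

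| n per group | d·√(n/2) | Test at 5% | z | Power, normal | Power, t |
|---|---|---|---|---|---|
| 80 | 2.530 | two-sided | 1.960 | Φ(0.570) = 71.6% | 71.0% |
| 80 | 2.530 | one-sided | 1.645 | Φ(0.885) = 81.2% | 80.9% |
| 100 | 2.828 | two-sided | 1.960 | Φ(0.868) = 80.7% | 80.4% |
| 100 | 2.828 | one-sided | 1.645 | Φ(1.183) = 88.2% | 88.0% |

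None of the four gives 85%. With 80 per group both tests fall short. With 100 per group the two-sided test falls short and the one-sided test overshoots. Changing alpha does not help at 80 per group: one-sided 10% gives 89.3% and two-sided 2.5% gives 60.6%.

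**Step 2: what 85% would require, unadjusted, two-sided 5%.**

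- Sample size at 0.4 SD: n = 2(1.960 + 1.036)²/0.4² = 112.2, so 113 per group by the normal approximation and 114 by the t distribution.
- Detectable difference: (1.960 + 1.036)·√(2/n) = 0.474 SD at n = 80 and 0.424 SD at n = 100. By the t distribution these are 0.477 and 0.426, which round to 0.48 and 0.43.

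**Step 3: unstated assumptions under which 0.4 SD does reach 85%, two-sided 5%.** Each method rescales the effect. The required correlation ρ is the value that brings the rescaled effect up to the detectable difference from step 2 (t distribution).

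| Method | Rescaled effect | n = 80 | n = 100 |
|---|---|---|---|
| ANCOVA on baseline | 0.4/√(1 − ρ²) | ρ ≥ 0.544 | ρ ≥ 0.343 |
| Change from baseline | 0.4/√(2(1 − ρ)) | ρ ≥ 0.648 | ρ ≥ 0.559 |
| Mean of 4 follow-up visits, compound symmetry | 0.4/√((1 + 3ρ)/4) | ρ ≤ 0.606 | ρ ≤ 0.843 |

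Check at n = 80: four visits with ρ = 0.6 give √((1 + 1.8)/4) = √0.70 and power 85.2%. ANCOVA gives 84.8% with ρ = 0.54 and 85.3% with ρ = 0.55.

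**Step 4: reconcile 80 with 100.** 80/(1 − 0.20) = 100, so 20% loss would link the two numbers. The Protocol states no such rate. Reading 80 as completers also leaves the unadjusted two-sided power at 71.0%.

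**The case against.** The strongest reply is that 71% rests on the reader's choices, not the protocol's. No alpha is stated, and a single-timepoint t-test is not the planned analysis. The protocol schedules a baseline and four follow-up HbA1c measurements and plans a mixed model. The correlations needed in step 3 are not extreme, and averaging four visits with a correlation of 0.6 gives 85.2% with 80 per group, almost exactly the stated figure. Alpha and the correlation structure may also be in a SAP that is not at hand.

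Much of this stands. The 85% cannot be called false, and the 71% is conditional. What remains is that the power paragraph mentions no repeated measures, adjustment or correlation, so nobody can check the number. The four-visit mean also estimates a time-averaged difference, whereas the primary outcome is HbA1c at 12 months. A protocol that states a power figure should state the alpha and method it depends on.

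On 80 against 100, the other side can say that the recruitment target is clear (200 appears throughout), that claiming power on fewer patients errs on the cautious side, and that *randomized* is probably a slip for *evaluable*. That limits the practical harm, since nobody would recruit the wrong number. It does not remove the contradiction, and a separate SAP cannot correct the protocol's own text. If all 100 per group are analysed, the unadjusted two-sided test still has 80.4% power for 0.4 SD, so the design itself is not in question.

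**Conclusion.** The concern holds in both parts.

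- **Contradiction.** 80 randomized per group conflicts with 100 randomized per group. This needs no assumption.
- **Power.** The 85% cannot be reproduced from the stated inputs. For an unadjusted two-sided 5% comparison, the shortfall at 0.4 SD is 14.0 percentage points with 80 per group (85 − 71.0) and 4.6 with 100 (85 − 80.4). Equivalently, 85% power corresponds to 0.48 SD or 0.43 SD. These sizes depend on the assumed alpha and on no gain from baseline or repeated measurements. With a suitable correlation, 85% is attainable at 80 per group, but the protocol does not claim one.

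**What to change.** Amend the Sample Size and Power paragraph as follows.

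1. Make the number randomized agree with 100 per group. If 20% loss is what was meant, say so: 100 randomized and 80 evaluable at 12 months per group.
2. State alpha and sidedness.
3. Then do one of the following:
   - Restate the power: *With 80 evaluable per group, an unadjusted two-sided 5% test has 71% power for 0.4 SD and 85% power for 0.48 SD.*
   - Or give the adjusted or longitudinal calculation for HbA1c at month 12 with its assumed correlation. For ANCOVA with 80 evaluable per group, 85% needs a baseline-to-month-12 correlation of about 0.55 (the exact threshold is 0.544).

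The cost is protocol wording only. No patients are added, and neither the design nor the analysis changes. The drawback is either a less favourable stated power or a commitment to a correlation that may prove too high.

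### The primary HbA1c model labels time only as random and ties no term to month 12, so as written it does not fix a valid test of the month-12 outcome

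*Protocol*

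**What the plan says.** The Analysis Plan takes the longitudinal HbA1c values as the response, "with intervention group (fixed effect), time (random effect), and time by intervention as the primary independent variables". Group is marked fixed, time is marked only random, and the interaction carries no label. Time is not said to be linear or categorical. The sentence before describes what such a model delivers: "MEM analyses estimate individual change in outcome for each subject in addition to estimating average change in outcome" within each group. That sentence also refers to four lettered groups, a clerical leftover in a two-arm trial.

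Elsewhere the target is a single time point. Research Strategy (Approach) states "The primary outcome will be HbA1c at 12 months post-randomization", and the Human Subjects section repeats it. Sample Size and Power claims that "we will have 85% power to detect at least a 0.4 standardized effect size", which it defines as a "difference in comparison group means in sd units".

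Three other places bear on the point:
- Entry requires "Clinical diagnosis of T2DM and HbA1c" of at least 8% at screening.
- Randomization is "stratified by clinical site, and baseline HbA1c levels".
- Description of Intervention has the telephone sessions run weekly for 12 weeks, so they end near month 3 of 12.

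**The concern.** Two separate problems follow from the model sentence.

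First, a mixed model needs a fixed time term, or its equivalent, to carry change common to both arms. Patient-level random slopes centred on zero do not do this. Without it, and with group coded 0/1, the usual-care mean is held flat and the interaction takes up the whole of the TIDES arm's change, including whatever usual care shows too. A common fall is plausible here because patients are selected on a high HbA1c. The payment paragraph ("Those considered ineligible at baseline will receive" a small sum) also suggests that eligibility is settled at baseline, so the qualifying value may be the baseline value.

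Second, even with fixed time, a linear time-by-group slope is a different quantity from the month-12 difference unless the effect builds linearly from zero. With sessions ending at 12 weeks, that cannot be presumed.

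Two analysts who both follow the sentence could therefore report different primary results.

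**Working it through.** **Inputs from the protocol:** visits at 0, 3, 6, 9 and 12 months; 80 per arm and 0.4 SD from the power statement. **Assumed, because the protocol gives none:** two-sided 5%, complete data, SD 1, and correlation between visits of 0.45 + 0.55 x 0.85^(lag in months), which is 0.53 between baseline and month 12.

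**1. The plan's own power figure.** For a plain comparison of means, SE = sqrt(2/80) = 0.158 and 0.40/0.158 = 2.53, giving 72% power, not 85%. With baseline adjustment the SE is multiplied by sqrt(1 - r^2), and 85% needs r of about 0.54, which is not stated. That mismatch is a separate matter. What counts here is that the calculation is for a difference in means, not in slopes.

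**2. Listed terms without fixed time.** The mean is b0 + b1·g + b2·g·t. With g = 0/1, the mean slope is 0 in usual care and b2 in TIDES. With no treatment effect, generalised least squares (GLS) gives:

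| Common fall (SD) | 12-month interaction estimate (SD) | Rejection, 0/1 coding | Rejection, fixed time added |
|---|---|---|---|
| 0.15, complete by month 3 | -0.14 | 26% | 5% |
| 0.25, complete by month 3 | -0.24 | 59% | 5% |
| 0.15, linear to month 12 | -0.15 | 28% | 5% |
| 0.25, linear to month 12 | -0.25 | 64% | 5% |

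Coding group as -0.5/+0.5, or testing an explicit difference between arm slopes, also gives 5%. Simulated fits with random intercepts and slopes (400 trials per case) gave 18% to 58% for 0/1 coding and about 5% for the valid forms. Two other assumed covariances gave 19% to 80% for 0/1 coding.

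**3. Is a fall of that size plausible?** Under bivariate normality, selection above a cut-off z (in clinic SDs from the clinic mean) gives an expected fall, in SDs of enrolled patients, of (1 - r) x λ(z) / SD_truncated. For z = 0 and repeat correlation 0.9, this is 0.1 x 0.798/0.603 = 0.13. Across z from -0.5 to +0.5 and r from 0.8 to 0.9, the range is 0.07 to 0.44. This presumes that the qualifying value is the baseline value.

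**4. Fixed but linear time.** Let t = 0, 0.25, 0.5, 0.75, 1, so Σ(t - 0.5)^2 = 0.625. The true month-12 effect is set at 0.40 SD.
- Early and sustained (0, 0.4, 0.4, 0.4, 0.4): slope x 12 = 0.200/0.625 = 0.32; fitted month-12 value = 0.32 + 0.5 x 0.32 = 0.48.
- Waning (0, 0.60, 0.53, 0.47, 0.40): slope x 12 = 0.167/0.625 = 0.27; fitted month-12 value = 0.40 + 0.5 x 0.27 = 0.53.
- Linear onset: 0.40 and 0.40.

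Under the assumed covariance, GLS narrows the gap: 0.38 and 0.46 for the sustained effect, 0.37 and 0.51 for the waning one. A month-12 contrast from categorical visits gives 0.40 in all three cases.

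**5. Value of baseline adjustment.** For a month-12 difference of 0.40 SD at 80 per arm, power is 72% unadjusted, 76% at r = 0.3, 85% at r = 0.53 and 89% at r = 0.6.

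**The case against.** The strongest reply is that coding, contrast and covariance belong in a statistical analysis plan, which is not at hand. The sentence calls itself a basic procedure, and it never names time-by-intervention as the primary test. Its neighbour says the model estimates average change in each group, which implies fixed trends, so time as a random effect is probably shorthand for random slopes. Under that reading the false-rejection rate is 5%. The linear-time gap likewise rests on a coding that the text does not state: with categorical visits, the group-by-visit terms already contain the month-12 contrast.

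Much of this stands. A missing contrast alone would not be a point. What remains is that the protocol commits to a model statement that leaves out the common trend, sits badly with the sentence before it, and is not connected to the month-12 outcome. An analysis plan that copies it inherits the fault.

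Three stronger readings are tempting and not supported:
- *The trial's primary test has a 26% to 64% error rate.* It has that rate only if fixed time is dropped, group is coded 0/1, the interaction is the test, and the assumed falls occur.
- *The rate reaches 37% to 84%.* Those rates come from a two-degree-of-freedom test of whether either arm changed, which is not a treatment comparison.
- *Any literal reading fails badly.* If time is a visit effect shared by all patients, it absorbs much of the common fall. With its variance set near that of the assumed visit means, rejection under 0/1 coding drops to roughly 7% to 15%, depending on how that variance is set.

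**Conclusion.** The point holds as a specification fault that should be fixed, with medium confidence. It does not show that the trial is invalid. As written, the model sentence lists time only as random and names nothing that estimates the month-12 difference which the protocol makes primary and uses for power.

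On the unfavourable but ordinary reading (no fixed time, 0/1 coding, interaction tested), false rejection is about 26% to 64% for common falls of 0.15 to 0.25 SD. On the charitable reading with linear time, the slope test is valid but can miss the target: slope x 12 is 0.32 or 0.27 by least squares, or 0.38 or 0.37 by GLS, for a true 0.40 SD. With fixed categorical visits and a month-12 contrast, neither problem arises. The sizes rest on the assumed SDs, correlations, falls and effect shapes. The direction of the first problem does not, given that coding and a common fall.

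**What to change.** In the Analysis Plan, replace the model terms with wording such as:

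> Post-baseline HbA1c (months 3, 6, 9, 12) will be modelled with fixed effects for group, visit (categorical) and group-by-visit, with baseline HbA1c and baseline-by-visit as covariates, and patient-level random effects or an unstructured covariance for within-patient correlation. The primary test is the TIDES minus usual-care difference at month 12.

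An equivalent form keeps baseline in the response with a mean common to both arms. Baseline must not be both response and covariate: with a coefficient of 1 the baseline value would be fitted exactly, and the fit degenerates under an unstructured covariance. Other forms of fixed time are acceptable if the month-12 contrast is named. Separately, change the reference to four lettered groups to the two arms.

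The cost is wording and a few degrees of freedom. No new data are needed, since baseline HbA1c is already collected and used for stratification. The gain is a test of the stated outcome that does not count shared change, with added precision from baseline.
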